Maslovitz et al. (31) reported the rate of vaginal bleeding of 1.8% following transcervical Foley catheter insertion. However, the bleeding was minor with unaltered haemoglobin levels and coagulation profile. There was also no case of cervical tear which might result in postpartum haemorrhage. Besides, risk of change of fetal vertex presentation to breech was reported to be 1.3% (31). This was probably related to concomitant presence of unengaged free-floating fetus and contraction following Foley catheter insertion which resulted in flipping movement of the fetus. Risk of poor APGAR and NICU admission was not significantly higher compared to other IOL methods eg. prostaglandin and oxytocin (24, 26).

Till date, there is paucity of evidence on the superiority of membrane sweeping and transcervical Foley catheter in IOL in previous Caesarean delivery. Both methods have the same mechanism action by increasing local production of endogenous prostaglandin (1). The aim of this study is to evaluate the effectiveness of membrane sweeping and transcervical Foley catheter insertion for IOL in women with previous Caesarean delivery.

OBJECTIVES AND PURPOSE

1. General objective:
 - a. To compare the effectiveness of membrane sweeping and transcervical Foley catheter for IOL in women with one previous Caesarean delivery.

2. Specific objectives:

- a. To compare the following induction outcomes between membrane sweeping and transcervical Foley catheter for IOL in women with one previous Caesarean delivery.
 - i. Improvement of modified Bishop score at interval of 24 hours and 48 hours, respectively.
 - ii. The requirement of oxytocin following IOL.
- b. To compare the following delivery outcomes between membrane sweeping and transcervical Foley catheter for IOL in women with one previous Caesarean delivery.
 - i. Mode of delivery.
 - ii. Overall:
 - Induction to delivery interval.
 - Oxytocin augmentation duration.
 - iii. Vaginal delivery subgroup:
 - Induction to delivery interval.
 - Amniotomy to delivery interval.
 - Duration of oxytocin augmentation.
 - Vaginal delivery rate within 24 hours of induction.
 - Vaginal delivery rate between 24-48 hours of induction.
- c. To compare the maternal outcomes between membrane sweeping and transcervical Foley catheter for IOL in women with one previous Caesarean delivery.
 - i. Uterine hyperstimulation.
 - ii. Uterine rupture.
 - iii. Post-partum haemorrhage.
 - iv. Maternal pyrexia.
 - v. Duration of hospitalization.

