 - i. Subjects may withdraw voluntarily from study at any time upon their request.
 - ii. Subjects are inappropriately enrolled without fulfilling inclusion/exclusion criteria.
 - iii. Subjects develop spontaneous labour before IOL procedure is undertaken.
- b. Follow up process:
 - i. The withdrawn subjects will be managed according to local protocol under Department O&G, Sibu Hospital.
 - ii. The withdrawn subjects data will be destroyed as it will not be used for data analysis.
- c. The withdrawn subjects will be replaced with new subjects in order to meet the required sample size.

TREATMENT AND PROCEDURES

1. Treatment and medications that are permitted during the trial:
 - a. Amniotomy
 - b. Oxytocin augmentation when contractions are not optimised
 - c. Abdominal and vaginal examination to assess labour progress
 - d. Intrapartum continuous fetal heart rate monitoring
 - e. Fetal scalp sampling in the presence of non-reassuring fetal heart rate
 - f. Instrumental delivery or emergency Caesarean section if indicated

2. Both IOL methods of membrane sweeping and transcervical Foley catheter do not contain drug or medication. Thus, the risk of uterine rupture is similar to spontaneous labour in women with previous Caesarean delivery. If scar dehiscence is highly suspected during labour, standard management with recourse to emergency Caesarean section will be undertaken.

3. Treatment and medications that are not permitted during the trial:
 - a. Vaginal prostaglandin E2

ASSESSMENT OF EFFICACY

1. Primary outcome:
 - a. Overall induction to delivery interval.
2. Secondary outcomes:
 - a. Induction outcomes:
 - i. Improvement of modified Bishop score at interval of 24 hours and 48 hours after induction.
 - ii. Whether oxytocin augmentation is required.
 - b. Delivery outcomes:
 - i. Mode of delivery.
 - ii. Duration of oxytocin augmentation overall and in vaginal delivery group.
 - iii. Induction to vaginal delivery interval.

- iv. Amniotomy to vaginal delivery interval.
- v. Vaginal delivery rate within 24 hours of induction and between 24-48 hours of induction.
- c. Maternal outcomes:
 - vi. Uterine hyperstimulation (> 5 contractions per 10 minutes for at least 20 minutes or a contraction lasting at least 2 minutes with/without abnormal fetal heart rate).
 - vii. Uterine rupture.
 - viii. Post-partum haemorrhage (estimated blood loss \geq 500 ml).
 - ix. Maternal pyrexia (temperature >38.0 °C once, or 37.5 °C on two occasions 2 hours apart).

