 - i. No further membrane sweeping will be performed.
 - ii. Affected subject will be withdrawn from the study.
 - iii. No rescue medication is needed as condition is self-limiting.
 - iv. Closed monitoring of vital signs and oxygen saturation for 24 hours.
 - c. Cervical tear
 - i. Examination under anaesthesia will be performed immediately.
 - ii. Cervical repair will be performed.
 - iii. Subject will be followed up till 42 days post-delivery (completion of puerperal period).
 - d. Uterine rupture
 - i. Emergency laparotomy will be performed immediately.
 - ii. Depend on the severity of uterine rupture, uterine repair or hysterectomy may be warranted.

- iii. Subject will be followed up till 42 days post-delivery (completion of puerperal period).
 - e. Maternal sepsis
 - i. Blood culture and high vaginal swab for culture will be taken.
 - ii. Broad spectrum antibiotics will be started as rescue medication.
 - iii. Unstable subjects will be nursed in intensive care unit.
 - iv. Subject will be followed up till 42 days post-delivery (completion of puerperal period).
5. Compensation of adverse events
- a. In the event of a bodily injury or illness directly resulting from the membrane sweeping or transcervical Foley catheter insertion, the department will pay for reasonable and necessary treatment.
 - b. The department is not responsible for medical expenses due to pre-existing medical conditions, any underlying diseases, any ongoing treatment process, subjects' negligence or willful misconduct, the negligence or willful misconduct of the investigators or the study site or any third parties.

STATISTICS

1. All results will be analysed using the Statistical Package for Social Sciences for Windows (SPSS for Windows).
2. Normality of numerical data (Bishop score, induction to delivery interval, induction to vaginal delivery interval, amniotomy to vaginal delivery interval, duration of oxytocin augmentation, duration of hospitalisation, APGAR score at 5 minutes, cord pH, neonatal birth weight) will be assessed using Kolmogorov-Smirnov analysis. Independent T-test (data with normal distribution) or Mann-Whitney U test (if data not normally distributed) will be used to compare these outcomes between the group of membrane sweeping and group of transcervical Foley catheter.
3. Chi-square test will be used to compare:

- a. The requirement of oxytocin augmentation following induction between the group of membrane sweeping and group of transcervical Foley catheter.

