- b. The following delivery outcomes between the group of membrane sweeping and group of transcervical Foley catheter.
 - i. Mode of delivery.
 - ii. Vaginal delivery within 24 hours of induction.
 - iii. Vaginal delivery within 24-48 hours of induction.
 - iv. The maternal outcomes (uterine hyperstimulation, uterine rupture, post-partum haemorrhage, maternal pyrexia) between the group of membrane sweeping and group of transcervical Foley catheter.

If there is at least one expected value of < 5 , Yates correction will be done.

If sample size is less than 20 or (>40 but at least one expected value <5), Fisher test instead of Chi-square test will be used.

4. Statistical significance is defined as p value < 0.05 .

CONFIDENTIALITY AND SECURITY OF SOURCE DOCUMENTS AND STUDY DATA

1. All of the subjects' information obtained in this study will be kept and handled in a confidential manner. When publishing or presenting the study results, subjects' identity will not be revealed without their expressed consent.
2. Data from the study will be archived and may be transmitted outside the country for the purpose of analysis, but subjects' identity will not be revealed at any time.
3. Following the trial, only the principal and co/sub investigators, and regulatory authorities but not the subjects have access to study data and findings.
4. Storage and archival of medical records and study data:
 - a. Medical records will be kept in the hospital record office as following hospital policy. The investigators will only keep the study data.

- b. Documents and other study materials can be accessed by staff restricted to the investigators and regulatory authorities.
- c. All data and documents or study materials will be made available whenever it is requested by relevant authorities, in the presence of investigator.
- d. Duration of study data storage will be 5 years after completion of study. Study data will be destroyed after period of storage.

FINANCE AND INSURANCE

1. This study is self-funded by Department of O&G, Sibug Hospital.

PUBLICATION POLICY

1. When publishing or presenting the study results, subjects' identity will not be revealed without their expressed consent in order to protect subjects' confidentiality.
2. Data from the study will be archived and may be transmitted outside the country for the purpose of analysis, but subjects' identity will not be revealed at any time.

INVOLVEMENT OF VULNERABLE SUBJECTS

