b) After 48 hours of induction

(only applicable to Foley group)

Achieved favourable Bishop (≥ 8) score: *(please tick)*

Yes

No

(if yes, proceed to sub-question;

if no, proceed to next question)

a) Interval to achieve favourable Bishop score

_____ (hours)

Achieved cervix allowing amniotomy: *(please tick)*

Yes

No

(if yes, proceed to sub-question;

if no, proceed to next section)

a) Bishop score at that time

b) Os dilatation at that time

_____ (cm)

c) Cervical length at that time

_____ (cm)

SECTION C: DELIVERY OUTCOMES

Oxytocin required during delivery (*please tick*) Yes No

Mode of delivery: (*please tick*)

- Vaginally Within 24 / 24-48 / > 48 hours of induction (*please circle*)
- Instrumentation Vacuum / forceps (*please circle*)
Indication: _____
- Caesarean section Indication: _____

Durations (regardless of final mode of delivery):

- a) Induction to delivery _____ (hours)
- b) Oxytocin augmentation _____ (minutes)

Durations (only for vaginal delivery including instrumental delivery):

- a) Induction to vaginal delivery _____ (hours)
- b) Amniotomy to vaginal delivery _____ (hours)
- c) Oxytocin augmentation _____ (minutes)

Estimated blood loss (EBL): ml

If EBL > 500ml, please mention cause: (*please tick*)

- a) Uterine atony
- b) Perineal trauma
- c) Retained placenta
- d) Coagulopathy
- e) Others *Please specify:*

Maternal complications: (*please tick*)

- a) Uterine rupture Yes No
- b) Uterine hyperstimulation Yes No
- c) Post-partum haemorrhage Yes No
- d) Maternal pyrexia Yes No

Neonatal outcomes:

- a) APGAR score at 5 minutes _____ To: NICU / SCN / mother (*please circle*)
- b) Cord pH _____
- c) Birth weight _____

SECTION D: MATERNAL SATISFACTION

If you had to repeat it all over again, would you take part in the study? (*please tick*)

Yes

No

If no, please provide reason(s). _____

Notes:

Uterine hyperstimulation : > 5 contractions per 10 minutes for at least 20 minutes or a contraction lasting at least 2 minutes with/without abnormal fetal heart rate

Post-partum haemorrhage : Estimated blood loss \geq 500 ml

Maternal pyrexia : Temperature >38.0 °C once, or 37.5 °C on two occasions 2 hours apart

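### Secondary comparisons use groups fixed after randomisation, no cumulative 48 h vaginal delivery rate is planned, and withdrawn women's study data are destroyed, so the planned dataset cannot support an all-randomised analysis

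*Combined protocol and SAP*

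**What the plan says.** **Durations.** The primary outcome is "Overall induction to delivery interval" (Assessment of Efficacy, 1.a). Appendix 3, Section C records it under "Durations (regardless of final mode of delivery", together with one oxytocin duration. A second set sits under "Durations (only for vaginal delivery including instrumental delivery": induction to vaginal delivery, amniotomy to vaginal delivery, and oxytocin duration again. The secondary outcomes include "Duration of oxytocin augmentation overall and in vaginal delivery group". Statistics, item 2, lists "induction to vaginal delivery interval, amniotomy to vaginal delivery interval" among the variables to be compared between arms by t-test or Mann-Whitney test.

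**Rates.** The secondary outcomes include "Vaginal delivery rate within 24 hours of induction and between 24-48 hours of induction". Statistics, item 3.b, gives "Vaginal delivery within 24-48 hours of induction" its own chi-square test beside the 24 h test, and lists no test for 0 to 48 h. Objectives 2.b.iii places both rates under "Vaginal delivery subgroup", and Table 3 places them under vaginal delivery. Statistics says only that the two groups are compared.

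**Bishop score.** Table 2 compares scores at 24 h and 48 h. Under Trial Design 5.m, a woman whose cervix is favourable at the 24 h check goes to amniotomy. The others have a second day, with further sweeping in Group 1 and conservative management in Group 2.

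**Withdrawals.** Consent is taken at admission, the envelope is opened once consent is signed, and induction follows the next morning (Trial Design 5.c, 5.f, 5.h). Spontaneous labour before the procedure is a withdrawal criterion. Data of withdrawn women are destroyed and the women replaced (Selection and Withdrawal 6.a.iii, 6.b.ii, 6.c). Among the listed adverse events, only a vasovagal attack after sweeping leads to withdrawal (Assessment of Safety 4.b.ii). Medical records stay in the hospital record office (Confidentiality, 4.a).

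**The concern.** The secondary endpoints are meant to show which method induces labour better. Several of them compare groups that randomisation did not create.

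- Having a vaginal birth is itself a trial outcome. If Caesareans fall mainly on slower labours, the arm with more Caesareans loses more of its slow labours from the vaginal-only comparison and looks faster.
- In the 24-48 h band, a method that moves deliveries from the second day to the first loses successes, so a faster method can score worse.
- The 48 h Bishop comparison largely leaves out women who went to amniotomy or delivered after the 24 h check. This tends to shrink a true difference.
- The withdrawal rule removes women who already have an allocation, in an unblinded trial. It reaches the primary comparison as well as the secondary ones.

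**Working it through.** The plan states no final sample size, SD or 24 h rate, so there is no figure of its own to reproduce. The sizes below are illustrations.

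**1. Vaginal-only durations.**

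Inputs from the Background section: vaginal birth rates of 56.1% (sweeping, a randomised trial) and 43.5% to 71.4% (Foley). A second sweeping study gives 17.3%, which the protocol links to Caesareans on maternal request; it is not used here.

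Assumed: SD 16 h and 64 per arm. The plan's formula, with constant 7.85 (two-sided 0.05, power 0.80), gives 64 when the SD is twice the difference to be detected: 1 + 2 × 7.849 × 2² = 63.8.

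Share left out of the vaginal-only tests: 1 − 0.561 = 43.9% for sweeping; 1 − 0.714 = 28.6% to 1 − 0.435 = 56.5% for Foley.

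Let labour times have the same normal distribution in both arms, and let Caesarean propensity correlate ρ with labour time. With a fraction q delivering vaginally, the mean among vaginal births falls below the overall mean by ρ × SD × φ(z_q)/q. The ratio φ(z_q)/q is 0.9049 at q = 0.435, 0.7028 at 0.561 and 0.4763 at 0.714.

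| Rates compared | Difference in ratio | ρ = 1 | ρ = 0.5 | ρ = 0.25 | ρ = 0 |
|---|---|---|---|---|---|
| 56.1% v 71.4% | 0.2265 | 3.62 h | 1.81 h | 0.91 h | 0 |
| 43.5% v 56.1% | 0.2021 | 3.23 h | 1.62 h | 0.81 h | 0 |

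Each entry is 16 × ρ × the difference, and is the apparent advantage of the arm with fewer vaginal births. At ρ = 1 it runs from 2.0 to 4.5 h for SDs of 10 to 20 h. In 4,000 simulated trials per setting, the t-test called that arm significantly better in about 4% of trials at ρ = 0.25 and 7 to 8% at ρ = 0.5, against 2.5% expected by chance.

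**2. The band, with all women as denominator.**

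Assumed counts of 64 per arm: Foley 20 by 24 h plus 15 in the band; sweeping 6 plus 26. All expected counts exceed 5, so the plan's plain chi-square applies: χ² = N(ad − bc)² / (product of the four margins).

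- 24 h, 20 v 6: 128 × 896² / (64 × 64 × 26 × 102) = 9.46, p = 0.002, favours Foley.
- Band, 15 v 26: 128 × 704² / (64 × 64 × 41 × 87) = 4.34, p = 0.037, favours sweeping.
- Cumulative, 35 v 32: 128 × 192² / (64 × 64 × 67 × 61) = 0.28, p = 0.60.

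With the same 35 Foley deliveries by 48 h but 19 of them early, the band gives p = 0.060.

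**3. The band, with vaginal births as denominator.**

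Assumed 46 Foley and 36 sweeping vaginal births (0.714 × 64 = 45.7; 0.561 × 64 = 35.9), with the same 35 and 32 delivered by 48 h. With 13 early Foley deliveries the band is 22/46 v 26/36: 82 × 404² / (46 × 36 × 48 × 34) = 4.95, p = 0.026. With 12 it is 23/46 v 26/36: 82 × 368² / (46 × 36 × 49 × 33) = 4.15, p = 0.042. The undefined denominator therefore changes the result materially.

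**4. Bishop score at 48 h.** No size can be fixed. Trial Design 5.m gives no score at which amniotomy becomes possible. Study Instruments 7.d says 8 or more generally means ripe, but Appendix 3 records reaching 8 and a cervix allowing amniotomy as separate items. The baseline spread is not given, and second-day care differs by arm.

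**5. Withdrawals.** Read together, the sections on allocation, induction timing and withdrawal mean that a woman who labours overnight has been randomised, is then withdrawn, and is replaced. A vasovagal attack can remove a woman from the sweeping arm only. The documents give no frequency for either event.

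**The case against.** The strongest defence is that the key comparison is sound in this respect. The primary interval and one oxytocin duration cover all modes of delivery, and Table 3 shows mode of delivery and Caesarean indication beside the durations. A reader might infer that every duration is restricted to vaginal births; the outcome list and Appendix 3 rule that out. What stands is that the primary counts a Caesarean as delivery and mode of delivery carries no time, so neither measures vaginal delivery over time.

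The band can also be called presentational. Appendix 3 records under 24, 24-48 and over 48 h, and Table 3 prints the two early bands in adjacent rows, so a reader can add them. That stands as a route to repair, but the plan still tests the band and not the sum. How often the band would mislead cannot be said, because the documents give no 24 h rate.

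On withdrawals, a reader might infer that the result could never be checked in all randomised women, or that the loss is known to differ by arm. Neither is supported. Hospital records remain, and labour before either procedure has little route to depend on allocation. What stands is that the planned study dataset omits these women.

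Finally, a correlation of 1 is unrealistic, since Table 3 lists fetal distress, suspected scar dehiscence and other indications besides slow progress. The figures at ρ = 1 are a ceiling only.

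**Conclusion.** The concern holds in a limited form. The vaginal-only durations rest on a set decided after randomisation. The 24-48 h band can point against the faster method, and its denominator is undefined. The 48 h Bishop comparison is selective. The withdrawal rule, followed as written, leaves a dataset that cannot support an all-randomised analysis.

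The vaginal-only effect is modest at moderate correlations (0.8 to 1.8 h) and vanishes if Caesarean is unrelated to labour length. This rests on the assumed SD of 16 h, on equal labour times in the two arms, and on birth rates taken from separate cited studies. The band results rest on assumed counts. No magnitude should be quoted for the Bishop score, and no size of differential withdrawal can be derived. Apart from the withdrawal rule, the problem is confined to secondary outcomes.

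**What to change.** 1. Replace the separate 24-48 h test with cumulative vaginal delivery within 24 h and within 48 h, with all randomised women in each arm as the stated denominator. State time zero for women who labour before the procedure; time from randomisation is one option. Cumulative incidence of vaginal delivery with Caesarean as a competing event may be added beside the unchanged primary, but is optional.
2. Amend Selection and Withdrawal 6.b.ii so that data already collected on withdrawn women are kept where consent allows. For women not withdrawn at their own request, take mode and time of delivery from the hospital record, again where consent allows. Analyse these women in the allocated arm and report withdrawals and reasons by arm. Clinical handling stays as written. This change must come before any data are destroyed.
3. Label the vaginal-only durations and the 48 h Bishop score as descriptive.

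The cost is a few sentences and a little more analysis. Mode of delivery, the interval and the timing categories are already on the form. It has date and time of admission and discharge but not of randomisation or delivery, so time from randomisation would need two added fields. That clock also includes the overnight wait, which is planned alike in both arms.

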birth rate of 56.1% (13). Another comparative study by Ramya et al. reported much lower vaginal birth rate of 17.3% which could be explained by high rate of Caesarean Section for maternal request in this study (14). The average intervals from sweeping to labour onset and to delivery were about 2 days (14) and 4 days (9), respectively. Membrane sweeping did not increase the risk of maternal or neonatal infection, Caesarean section, postpartum haemorrhage and neonatal poor APGAR score, though discomfort during vaginal examination, minor vaginal bleeding and irregular contraction were frequently reported by women undergoing membrane sweeping (13, 15). No cases of uterine rupture was reported among women with scarred uterus undergoing membrane sweeping (14).

Pharmacological IOL method involving prostaglandin is avoided in SibU Hospital in view of higher risk of scar rupture and presence of limited number of consultants to cope with this debilitating event. Non-pharmacological methods of IOL such as Foley catheter, double-balloon catheter, hygroscopic cervical dilator (laminaria tent) etc are known to have lesser risk of scar rupture. Double-balloon catheters are limited in numbers in this hospital and they are costly. Laminaria tent is not available in this hospital. Foley catheter is a consumable item in this hospital and thus is readily available all the time. Compared to double-balloon catheter, Foley catheter has equivalent cervical ripening efficacy and safety profile (16). In addition, Foley catheter is also cheaper and has shorter induction to delivery interval. All these advantages make Foley catheter an ideal method of IOL for women with previous Caesarean delivery.

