 - x. Duration of hospitalisation.
- d. Neonatal outcomes:
 - i. APGAR score at 5 minutes.
 - ii. Cord pH.

ASSESSMENT OF SAFETY

1. No adverse events (AEs) will be expected during the course of study because there is no involvement of pharmacological drug or product. Both methods of membrane sweeping and transcervical Foley catheter do not contain drug or medication. Thus, the risk of uterine rupture is similar to spontaneous labour in women with previous Caesarean delivery. However, maternal discomfort and vaginal bleeding following membrane sweeping and unknown latex allergy following transcervical Foley catheter insertion may occur, and subjects will be informed of this risk in the informed consent.
2. All other invasive (amniotomy, fetal scalp sampling in the presence of non-reassuring fetal heart rate, instrumental delivery or emergency Caesarean section if indicated) and non-invasive procedures (maternal vital signs observation and intrapartum continuous fetal heart rate monitoring) and evaluations (abdominal and vaginal examination to assess labour progress) included in this protocol are considered to be standard of care in evaluation and management of women with one previous Caesarean delivery undergoing IOL and would have been performed as part of routine practice.

3. Report of adverse events eg. SAEs, SUSARs.
 - a. When adverse event of any type occurs, local SAE/SUSAR report will be created by principal investigator and notified via SAE Platform on NMRR website.
 - b. Subjects who experience SAE/SUSAR will be followed up by principal investigator and a follow up report will be submitted.
 - c. For “Non-life threatening SUSARs” eg. latex allergy associated with Foley catheter insertion, vasovagal attack following membrane sweeping, and cervical tear, initial report is to be submitted within 15 calendar days followed by a follow up report.
 - d. For “Life threatening SUSARs” eg. uterine rupture and maternal sepsis, initial report is to be submitted within 7 calendar days followed by a follow up report within the next 8 calendar days.

4. Process and duration of follow-up of adverse events
 - a. Latex allergy associated with Foley catheter insertion
 - i. Foley catheter will be removed immediately.
 - ii. Steroids and anti-histamine will be administered as rescue medication.
 - iii. Closed monitoring of vital signs and oxygen saturation for 24 hours.
 - b. Vasovagal attack following membrane sweeping

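### Procedure effects that the plan itself names for each arm have no dedicated form field, listed outcome or between-arm table, so a finding of similar maternal outcomes would not cover them

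*Combined protocol and SAP*

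**What the plan says.** **Effects named.** The background reports that "discomfort during vaginal examination, minor vaginal bleeding and irregular contraction were frequently reported by women undergoing membrane sweeping", without a rate. For the Foley catheter, a cited series "reported the rate of vaginal bleeding of 1.8% following transcervical Foley catheter insertion"; the bleeding is described as minor, with haemoglobin unchanged. In the same series the "risk of change of fetal vertex presentation to breech was reported to be 1.3" per cent. Assessment of Safety, item 1, adds that "maternal discomfort and vaginal bleeding following membrane sweeping and unknown latex allergy following transcervical Foley catheter insertion may occur" and states what follows from this: "subjects will be informed of this risk in the informed consent". Items 3.c and 4 of that section also name vasovagal attack after sweeping.

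**What is compared.** Objective 2.c lists hyperstimulation, rupture, post-partum haemorrhage, pyrexia and length of stay. The first four are also the complications in the secondary outcomes, the chi-square list, Table 3 and the form's tick-boxes under "Maternal complications" (Appendix 3, Section C). Length of stay is compared as a numerical outcome.

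**Other routes.** Assessment of Safety, 3.a: "When adverse event of any type occurs, local SAE/SUSAR report will be created by principal investigator". Section D of the form asks whether the woman would take part again (yes or no), with a free-text reason if not. Section C has a free-text line for the indication for Caesarean section.

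**The concern.** The two arms expose women to different procedures: sweeping twice a day, possibly for a second day, against one catheter left under traction for up to 24 hours (Trial Design, 5.i, 5.j and 5.m). The effects most closely tied to those procedures are the ones left without a field or a comparison. If the trial reports similar maternal outcomes, a reader choosing between the methods may take this to include discomfort and bleeding from the procedure. It would not, and the missing data could not be reconstructed afterwards.

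One named effect could also be lost outright. A woman with a vasovagal attack after sweeping is withdrawn (Assessment of Safety, 4.b), and withdrawn women's data are destroyed and not analysed (Selection and Withdrawal of Subjects, 6.b).

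**Working it through.** The plan states no figure on this point, so the main check is a trace of each named effect.

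| Effect | Where named | Own form field | Listed outcome | Test or table row | Indirect route |
|---|---|---|---|---|---|
| Discomfort, sweeping | Background; Safety 1 | no | no | no | Section D free text, only after a no |
| Bleeding, sweeping | Background; Safety 1 | no | no | no | adverse event report |
| Bleeding, Foley | Background (1.8%) | no | no | no | adverse event report |
| Change to breech, Foley | Background (1.3%) | no | no | no | indication line, only if Caesarean follows |
| Latex allergy, Foley | Safety 1, 3.c, 4.a | no | no | no | adverse event report |
| Vasovagal attack, sweeping | Safety 3.c, 4.b | no | no | no | adverse event report; trial data destroyed on withdrawal |

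None of the six has a dedicated field, outcome or row. The form's blood-loss item does not fill the gap: it serves post-partum haemorrhage (500 ml or more) and offers causes such as uterine atony and retained placenta. The 4-hourly checks (Trial Design, 5.l) cover contractions, temperature and fetal heart rate, but not bleeding, pain or presentation.

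**Expected counts.** The final sample size is not stated, and neither are s and d. The plan's formula is n = 1 + 2C(s/d)². I assume a two-sided test (the plan does not say), with α = 0.05 and power 0.8, so C = (1.960 + 0.842)² = 7.849. Before the dropout allowance:

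- d/s = 0.5 (assumed): 1 + 2 × 7.849 / 0.25 = 63.8, so 64 per arm.
- d/s = 0.3 (assumed): 1 + 2 × 7.849 / 0.09 = 175.4, so 176 per arm.

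Expected Foley events are n × p, and the chance of at least one is 1 − (1 − p)ⁿ:

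| Effect | 64 per arm | 176 per arm |
|---|---|---|
| Bleeding, 1.8% | 1.2 (69%) | 3.2 (96%) |
| Change to breech, 1.3% | 0.8 (57%) | 2.3 (90%) |

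**Could the sweeping effects be compared?** The documents give no rate, so every rate below except the 1.8% is an assumption. With n per arm and p̄ the mean of p₁ and p₂, power = Φ{[|p₁ − p₂| − 1.96√(2p̄(1 − p̄)/n)] / √([p₁(1 − p₁) + p₂(1 − p₂)]/n)}. For discomfort at 50% against 30% with n = 64: (0.2 − 1.96 × 0.0866) / 0.0848 = 0.357, which gives 64%.

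| Assumed rates | 64 per arm | 176 per arm |
|---|---|---|
| Bleeding 10% vs 1.8% | 50% | 91% |
| Bleeding 20% vs 1.8% | 92% | over 99% |
| Discomfort 50% vs 30% | 64% | 97% |
| Discomfort 50% vs 40% | 20% | 47% |

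Whether a sweeping comparison would be informative therefore depends on rates that the documents do not supply.

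**The case against.** The best defence is that objective 2.c is a closed list and the plan delivers it: all five items are collected, tested and tabulated. That stands. A reader might infer that the plan fails its own maternal objective, but the documents do not support this. The point concerns a useful extension, not a broken promise.

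Other tempting readings also go too far:

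- *That the plan says the methods cause these harms.* Its words are weaker: the effects were reported or may occur, and the mechanism for breech is offered as probable.
- *That the compared complications mostly arise in labour.* The documents do not say so. Contractions and temperature are checked every 4 hours after induction, so hyperstimulation and pyrexia during ripening can be seen.
- *That nothing captures these effects.* Adverse events of any type are to be reported, latex allergy and vasovagal attack have a 15-day reporting limit and follow-up steps, and a breech leading to Caesarean could be written as the indication and fall under the Others row in Table 3. What remains true is that none of these routes is a structured field completed for every woman, and no table sets the adverse event reports side by side by arm. The same safety section opens by expecting no adverse events, which makes even capture of minor effects unlikely.
- *That women are warned at consent about every effect listed here.* Safety item 1 ties consent to discomfort and bleeding after sweeping and to latex allergy only. The consent pages are not available, so no more can be said.

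Section D and objective 2.e (women's evaluation of care) come closest to covering tolerability. But one question about joining the study again measures neither discomfort nor bleeding, and it has no planned test or table.

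**Conclusion.** The point holds as a worthwhile, low-cost improvement. The named procedure effects have no dedicated field, listed outcome or between-arm table, so the trial could not support a statement about them in either direction. The outcomes that the plan does list are handled as written.

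The size is modest. At the cited rates and an assumed 64 to 176 women per arm, the Foley arm would have about 1 to 3 bleeds and 1 to 2 changes of presentation. These are counts to report, not to test. For sweeping, the plan says only that the effects are frequent. A reader might infer that a comparison is sure to be informative at these sizes, but without a rate that cannot be claimed. All counts rest on assumed arm sizes and on the cited rates applying to this population.

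**What to change.** Add three items to the form, completed in both arms at the 24-hour assessment and again at 48 hours or at amniotomy if induction continues:

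- vaginal bleeding since induction (yes/no);
- worst discomfort since induction (0-10), so that repeated sweeps and the indwelling catheter are both covered, which a single score after the first procedure would not do;
- non-cephalic presentation (yes/no).

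Tabulate allergic reactions and vasovagal attacks by arm from the adverse event reports. A tick-box alone would not secure the vasovagal events, because the form would be destroyed with the withdrawn woman's data. Selection and Withdrawal of Subjects, 6.b, and Assessment of Safety, 4.b, must therefore be reconciled so that these events are kept and counted by randomised arm. This concerns data retention only, not clinical management.

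Add the items to the secondary outcomes and to Table 3 as descriptive outcomes: counts with risk difference and 95% CI, and a mean difference with 95% CI for discomfort.

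The cost is slightly more data entry at contacts that already take place; the primary outcome, sample size and treatment do not change. Two limits should be stated in the report: the discomfort score is open to bias because the trial is unblinded (Trial Design, 5.g), and the Foley counts are too small for a useful test.
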